#### 12.5 Adverse Events

Each subject eye treated must be examined for the presence/absence of adverse events at all visits, whether scheduled or not. If an adverse event (AE) occurs, the first concern will be the safety and welfare of the subject. Treatment should be provided as appropriate for the event.

### 12.5.1 Adverse Events Definitions

For the purposes of this Clinical Investigation, adverse events include: all serious and non-serious AEs; ocular adverse device effects (ADEs; Serious Adverse Device Effect (SADE). AEs, SAEs, ADEs and SADEs are defined as follows.

An adverse event (AE) is any untoward medical occurrence, unintended disease or injury, or untoward clinical sign (including abnormal laboratory finding) in a subject, user or other persons, whether or not related to the investigational medical device and whether anticipated or unanticipated. This definition includes events related to the investigational medical device, Control or Comparator IOLs or procedures involved. For users or other persons, this definition is restricted to events related to the Investigational medical device or Control or Comparator IOLs.

A Serious Adverse Event (SAE) is an AE that leads to:

- Death
- A serious deterioration in the health of the subject that either results in:
  - a life-threatening illness or injury, or
  - a permanent impairment of a body structure or body function (e.g., blindness), or
  - in-patient or prolonged hospitalization, or
  - a potentially vision-threatening condition, or
  - medical or surgical intervention to prevent life- or vision-threatening illness or injury or permanent impairment to a body structure or a body function
- fetal distress, fetal death, or a congenital abnormality or birth defect

An Adverse Device Effect (ADE) is any adverse event related to the use of an investigational medical device. This definition includes any events resulting from insufficient or inadequate instructions for use, deployment, implantation, installation or operation, or any malfunction of the investigational medical device. This definition also includes any event resulting from use error or from intentional misuse of the investigational medical device. This definition also includes Control and Comparator IOLs.

A Serious Adverse Device Effect (SADE) is any ADE which also meets any of the serious criteria for SAEs.

SADEs include the following:

- Unanticipated is a serious adverse device effect which by its nature, incidence, severity or outcome has not been identified in the current version of the Risk Analysis Report.
- Anticipated is a serious adverse device effect which by its nature, incidence, severity or outcome has been previously identified in the Risk Analysis Report.

Anticipated AEs associated with cataract surgery and/or premium IOL implantation that might reasonably be expected to occur in this Clinical Investigation are listed below and include, but are not limited to, the following:

Anterior capsule tear

Anterior uveitis (including iritis and iridocyclitis)\*

Capsular block syndrome  
Choroidal detachment/hemorrhage  
Corneal edema\*  
Cystoid macular edema (CME) \*  
Difficulty with tasks in dim light\*  
Elevated IOP\*  
Endophthalmitis (intraocular inflammation requiring vitreous tap and use of intraocular antibiotics)  
Events resulting in unplanned secondary surgical intervention other than paracentesis to relieve pressure prior to 1 week postoperative or Nd:YAG capsulotomy  
Flat anterior chamber  
Hyphema  
Hypopyon  
Incorrect IOL power resulting in secondary surgical intervention\*  
Increased glare or halos  
Infectious keratitis  
IOL damage resulting in secondary surgical intervention\*  
IOL malposition resulting in secondary surgical intervention\*  
Iris or pupil damage  
Loss of BCVA\*  
Mechanical pupillary block (A shallowing of the peripheral and/or central anterior chamber with or without elevation of IOP by obstruction of the flow of aqueous humor from the posterior chamber through the pupil to the anterior chamber). This may be induced by the crystalline lens, vitreous face, or implanted devices.)  
Multiple (or “ghost”) images  
Pain\*  
Posterior capsular rupture  
Progression or onset of diabetic retinopathy  
Progression or onset of macular degeneration  
Reduced contrast sensitivity  
Retained lens material  
Retinal detachment (partial or complete RD associated with retinal tear)  
Secondary IOL intervention (reposition, exchange or removal)\*  
Synechiae formation  
Thermal injury (phaco burn)  
Toxic anterior segment syndrome (TASS) (An acute, noninfectious inflammation of the anterior segment of the eye that develops within 24 to 48 hours after surgery and is characterized by corneal edema and accumulation of white cells in the anterior chamber of the eye)

Undesirable optical phenomena resulting in secondary surgical intervention  
Vitreous prolapse  
Wound leak (positive Seidel)

\* These events may be considered normal or expected events after cataract surgery and only need to be reported as AEs/SAEs if present as specified below:

- Iritis/cells/flare characterized by grade 1+ cells or greater using SUN criteria  if persistent for greater than 3 months after surgery, or relapses in less than 3 months after discontinuation of therapy, or the subject is maintained on therapy for more than 3 months to control inflammation
- Corneal or corneal wound edema resulting in BCDVA of  $\leq 20/40$  at present at Visit 3
- Cystoid macular edema diagnosed by clinical exam and adjunct testing (eg. OCT, FA or other method), resulting in BCDVA of  $\leq 20/40$  at Visit 3 or later
- Elevation of IOP by  $\geq 10$  mmHg above baseline (pre-operative) to a minimum of 25 mmHg after Visit 1 or elevated IOP requiring treatment if present at Visit 3
- Postoperative refractive error different from predicted, and not due to calculation or other use error, resulting in secondary surgical intervention
- Crack, breakage or deformity of IOL haptic or optic resulting in secondary surgical intervention
- IOL decentration or tilt likely to affect visual outcome and resulting in secondary intervention
- Monocular BCDVA decrease of greater than 2 lines ( $>10$  letters) from any previous visit not secondary to any underlying condition, or any monocular BCDVA decrease from any previous visit of greater than 2 lines if persistent to the subject's last visit in the Clinical Investigation.
- Pain, per subjective patient reporting, graded on a VAS pain rating scale (from 0 to 10)
- Moderate superficial punctate keratitis (SPK) present at Visit 3 or severe, or very severe SPK at any post-operative visit (note: if SPK is present pre-operatively, adverse event must be reported only if there is a worsening)

Note: Posterior capsular opacification (PCO) is NOT to be reported as an adverse event unless PCO is treated with Nd-YAG laser exposure.

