#### 12.5.4.1 SAE, Reporting

The Principal Investigator must report any adverse event to the Sponsor and its representative in an expedited manner if it meets the criteria for an SAE/SADE, and any available supporting documents to the Sponsor or its designee within 24 hours of becoming aware of an event.

The Principal Investigator must also report SAE/SADE to the reviewing IRB/IEC and Regulatory Authority as required by local regulations. The Principal Investigator should also complete applicable CRFs within 3 working days of event identification. After first being informed by the Principal Investigator, the Sponsor or its representative will report the SADE to the Regulatory

Authority within the timelines required by local regulations, as described in the Clinical Investigation Safety Management Plan.

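### The starred-event footnote in 12.5.1 applies its time windows to SAEs as well as AEs, which contradicts the SAE definition and the SAE reporting rules

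*Combined protocol and SAP*

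**What the plan says.** Section 12.5.1 lists anticipated adverse events and stars some of them, including anterior uveitis, corneal edema, cystoid macular edema (CME) and elevated IOP. The footnote describes starred events as possibly normal or expected after cataract surgery and says they "only need to be reported as AEs/SAEs if present as specified below". The criteria for the four events named are:

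- **Iritis** of grade 1+ cells or more: reportable "if persistent for greater than 3 months after surgery, or relapses in less than 3 months after discontinuation of therapy", or if "the subject is maintained on therapy for more than 3 months to control inflammation".
- **Corneal edema**: reportable if it reduces BCDVA to the stated level and is present at Visit 3.
- **CME**: reportable if it reduces BCDVA to the stated level "at Visit 3 or later".
- **IOP**: reportable for a rise of at least 10 mmHg above baseline "to a minimum of 25 mmHg after Visit 1 or elevated IOP requiring treatment if present at Visit 3".

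The SAE definition, also in 12.5.1, covers potentially vision-threatening conditions and "medical or surgical intervention to prevent life- or vision-threatening illness or injury or permanent impairment to a body structure or a body function". It sets no time limit. Section 12.5.2 sends every AE, serious or not, to the CRF. Section 12.5.4.1 states: "The Principal Investigator must report any adverse event to the Sponsor and its representative in an expedited manner if it meets the criteria for an" SAE or SADE, with a limit of 24 hours from awareness. None of these three rules makes an exception for starred events.

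**The concern.** A filter that keeps routine postoperative findings out of the AE tables is ordinary. This one names SAEs explicitly, and its criteria contain no exception for an event that is serious. For one and the same event, a site can find one instruction that reporting is not needed and another that a report is due within 24 hours.

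The events concerned are central to the safety evaluation. Section 12.4 lists ten risks of IOL implantation, and four of them are of the filtered types: macular edema, corneal edema, iritis and raised IOP requiring treatment. The synopsis includes safety in the objective, and section 13.2.1 tabulates SAEs by treatment group. If a site follows the footnote, serious events of these types can drop out of both the expedited route and those tables.

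**Working it through.** No sample-size or power figure bears on this point. The check sets the sections side by side and follows each event through them.

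**Step 1. Scope of the footnote.** It restricts reporting as an AE and as an SAE. On its wording, therefore, the criteria govern serious events too.

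**Step 2. Which events fall outside the criteria.** Section 7.3 puts Visit 3 at about 3-5 months after surgery. The day of Visit 1 is redacted.

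| Event | Outside the footnote's criterion when |
|---|---|
| CME | it has cleared before Visit 3 |
| Corneal edema | it has cleared before Visit 3 |
| Iritis | it resolves within 3 months, needs no more than 3 months of therapy, and does not relapse within 3 months of stopping therapy |
| IOP | it occurs up to Visit 1; or it occurs later, stays below the 10/25 mmHg thresholds and is no longer present at Visit 3 |

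The IOP criterion has two limbs. The first (at least 10 mmHg above baseline and at least 25 mmHg, after Visit 1) has no persistence condition, so such a rise is reportable even if it is treated and resolves. Attaching the Visit 3 condition to this limb as well would make its reference to Visit 1 redundant.

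The iritis cut-off is 3 months, not Visit 3. An iritis that lasts longer than 3 months but is gone by a later Visit 3 is reportable.

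**Step 3. The same events under the other rules.** Suppose any event in the right-hand column also meets a seriousness criterion. It is then an SAE under the definition, goes in the CRF under 12.5.2, and is due within 24 hours under 12.5.4.1. The footnote says it need not be reported. No section states which rule prevails. The iritis rule also cannot work alongside the expedited clock, because persistence beyond 3 months cannot be known within 24 hours of awareness.

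**Step 4. Whether other items close the gap.**

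- Hypopyon, endophthalmitis and toxic anterior segment syndrome (TASS) are listed without a star, so they are captured.
- Unplanned secondary surgical interventions are captured, except Nd:YAG capsulotomy and paracentesis to relieve pressure before 1 week. A pressure spike up to Visit 1 that is relieved by paracentesis in the first week is outside both this item and the IOP criterion.
- Hospitalizations are captured as SAEs under 12.5.2 until the cause is identified.
- The loss-of-acuity item is not a backstop for CME. A drop "from any previous visit not secondary to any underlying condition" counts at any visit, but a drop caused by an underlying condition counts only if it persists to the subject's last visit.

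These items narrow the gap and leave part of it open.

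**Step 5. Sensitivity of the SAE table.** One omitted subject changes an arm's SAE rate by 1/30 = 3.3 percentage points in an arm of 30, and by 1/20 = 5 points in the arm of 20. This shows only how much a single subject weighs. It is not a predicted number of omissions.

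**The case against.** The strongest reply is that two unqualified rules already require these reports. Section 12.5.2 covers all AEs, 12.5.4.1 covers any event meeting the SAE criteria, and Appendix D gives the reporting of all AEs as the reason for the Version 2.0 changes. A site that left out an SAE would breach both sections. The footnote can also be read narrowly: a vision-threatening event is hard to call normal or expected, and several severe presentations are listed separately without a star.

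This reply stands in part. A reader might infer that serious CME, iritis or raised IOP resolving before Visit 3 need never be reported. The documents do not support that, because 12.5.2 and 12.5.4.1 say the opposite; the defect is a contradiction, not a clean exemption. A reader might also infer that every IOP spike gone by Visit 3 escapes. That is wrong for rises after Visit 1 that meet the 10/25 mmHg thresholds. Nor does severe uveitis leading to admission escape, since the hospitalization rule in 12.5.2 catches it, at least until the cause is identified.

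The reply does not remove the conflict. The footnote is the more specific instruction and names SAEs, so a site could reasonably follow it. Section 12.5.2 itself refers to test results that meet the plan's requirements for classification as an AE, which points back to these criteria.

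On consequences, it is fair to say that there is no safety hypothesis test, that the same footnote applies in all three arms, and that IOP, slit-lamp, fundus, OCT and acuity findings are collected as clinical parameters. Most safety variables are redacted. It therefore cannot be said that these events would vanish from the safety evaluation.

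**Conclusion.** The concern holds as an internal contradiction in safety reporting. It is confined to starred events that meet a seriousness criterion but fall outside their window, as tabulated in the working. For CME and corneal edema the window opens only at Visit 3, so the conflict covers nearly all of follow-up. For iritis the 3-month persistence and therapy conditions leave most of it, with relapse as a separate route to reporting. For IOP the part up to Visit 1 has unknown length because the visit day is redacted.

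SAE counts may be incomplete. The documents give no event rates and no basis for predicting how sites would resolve the conflict, so the size of the effect cannot be estimated. The conclusion rests on reading the footnote as written and on reading the Visit 3 condition as belonging only to the second IOP limb. The Safety Management Plan and CRF guidance are separate documents that were not available; they may give further instruction, but the protocol should not contradict itself.

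This should be corrected: a stated rule, if followed, takes serious events out of expedited reporting and out of the SAE tables, and the correction is cheap.

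**What to change.** Delete /SAEs from the footnote in 12.5.1 and add a sentence such as: a starred event that meets any SAE criterion in 12.5.1 is recorded and reported under 12.5.4.1 regardless of the time windows below. The windows then filter only non-serious expected events.

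Align the all-AE rule in 12.5.2 with the footnote by a cross-reference, so that the treatment of non-serious starred events outside the criteria is also unambiguous. Make the CRF guidance match.

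The clinical thresholds and windows stay as they are, and no treatment rule is touched. The cost is one added sentence, a cross-reference, matching guidance, and possibly a few more SAE forms.

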#### 12.4 Risk Assessment, Risk Mitigation, and Anticipated Benefit

The model EA IOL and MX60E IOL have similar chemical and mechanical properties to the FDA approved model MX60 IOL that has been shown to be safe for implantation in humans

The known risks of implanting the enVista refractive enhanced monofocal EA IOL are generally the same as the risks of the enVista MX60E monofocal IOL. However, there may be a symptomatic reduction in the quality of distance vision with the EA IOL because more light is being redirected to provide a tolerance to distance defocus, and potential risks may include the following:

- Under scotopic and mesopic conditions, the patient may have [REDACTED]

Therefore, the candidacy of patients with amblyopia or abnormalities of the cornea, optic disc, and macula must be carefully considered. Although likely uncommon, explantation of EA IOLs may become necessary if optical side effects are intolerable.

The risks associated with IOL implantation following cataract surgery are developed through many years of successful use as demonstrated through the development of an ISO standard for clinical trials.

- Cystoid macular oedema
- Hypopyon
- Endophthalmitis
- Lens dislocated from posterior chamber
- Pupillary block
- Retinal detachment
- Secondary surgical intervention
- Corneal stroma oedema
- Iritis
- Raised IOP requiring treatment

Patients implanted with the EA IOL might benefit from the enhancing depth of focus of this lens comparable with the potential benefit provided by the [REDACTED] IOL comparator lens.

The risks and benefits must be weighed on an individual basis by the Principal Investigator in consultation with each potential subject. Ensuring the subject understands the risks and benefits of the Clinical Investigation and EA IOL is an important part of the risk mitigation.

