### 12.5.2 Identification and Collection

Identification and collection of an AE begins after informed consent has been obtained and documented. Standard sources of identifying AEs include:

- direct observation by the Principal Investigator
- asking the Clinical Investigation participant a non-specific question (e.g., "Have you had any problems since the last visit?")

- volunteering of information by the Clinical Investigation participant (e.g., “Doctor, I have had blurred vision since I started using this lens.”)
- laboratory or test results that meet CIP requirements for classification as an AE.

All AEs, non-serious and serious, observed or elicited by the Principal Investigator, reported by the subject, or resulting from a test result, etc., occurring during the clinical investigation must be reported in the CRF. During the Clinical Investigation, the Principal Investigator should treat the Clinical Investigation subject as appropriate to ensure his/her safety and welfare.

Pre-existing conditions will not be considered AEs but will be collected at the Preoperative Visit as medical history. A worsening of a pre-existing condition during the Clinical Investigation should be documented as an (S)AE and evaluated accordingly.

Hospitalizations should be captured as a SAE until the cause of hospitalization can be identified. The following reports of hospitalization without a medical AE should not be considered either serious or an AE:

- Planned hospitalization for pre-existing condition, or a procedure required by the CIP, without a serious deterioration in health, is not considered a serious adverse event (e.g., for work-up of persistent pretreatment lab abnormality).
- Social admission (e.g., subject has no place to sleep)
- Administrative admission (e.g., for yearly physical exam)
- Optional admission not associated with a precipitating ocular medical AE (e.g., for elective cosmetic surgery)

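### One adverse event term, difficulty in dim light, is made reportable only against a criterion the protocol never gives, in conflict with its all-AE rule

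*Combined protocol and SAP*

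**What the plan says.** Section 12.5.1 lists anticipated AEs and marks some with an asterisk. The footnote explains the mark: "These events may be considered normal or expected events after cataract surgery", and they "only need to be reported as AEs/SAEs if present as specified below". One of the marked terms is "Difficulty with tasks in dim light". The criteria that follow run from "Iritis/cells/flare characterized by grade 1+ cells or greater using SUN criteria" to "Moderate superficial punctate keratitis (SPK) present at Visit 3".

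Section 12.5.2 sets the general collection rule and makes no reference to the footnote. It covers "All AEs, non-serious and serious, observed or elicited by the Principal Investigator, reported by the subject" or arising from a test result, and makes their entry in the CRF mandatory.

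Section 12.4 describes the Test lens's risks as broadly those of the Control lens, with an exception: "there may be a symptomatic reduction in the quality of distance vision with the EA IOL". It then lists a potential risk under scotopic and mesopic conditions, with the symptom blacked out.

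Section 13.2.1 summarises the treatment-emergent AEs that were reported and compares the arms by tabulating subjects with one or more AEs.

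**The concern.** The asterisk is a filter: a marked event becomes reportable once it passes its listed criterion. For dim-light difficulty there is no criterion to pass, so the footnote taken alone never triggers reporting. Section 12.5.2 points the other way. A site has to choose between the two rules, and different staff, or the same staff on different occasions, could choose differently.

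Safety is among the objectives in the Synopsis, and adverse events head the list of safety variables in section 12.3. The AE tables can show only what was entered. Low light is also a condition that section 12.4 singles out for the Test lens. If the term is left out or entered erratically, a low count in any arm cannot be told apart from a reporting convention. Under section 9.1.1.1 the Principal Investigator and the implanting Sub-Investigators know the assignment, and under section 12.5.3 the Principal Investigator evaluates AEs. Any discretion over whether to record the symptom may therefore rest with someone who is not masked.

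**Working it through.** No sample size, power or error rate enters this point. The check is a cross-match of each asterisked term in section 12.5.1 against each criterion printed below the footnote.

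| Asterisked term | Criterion below the footnote |
|---|---|
| Anterior uveitis | Yes (iritis, cells, flare) |
| Corneal edema | Yes |
| Cystoid macular edema | Yes |
| Difficulty in dim light | **None** |
| Elevated IOP | Yes |
| Incorrect IOL power | Yes (refractive error) |
| IOL damage | Yes |
| IOL malposition | Yes (decentration or tilt) |
| Loss of BCVA | Yes |
| Pain | Yes (a scale is named, without a cut-off) |
| Secondary IOL intervention | None of its own, but covered elsewhere |

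1. Terms: 9 with their own criterion + 2 without = 11 asterisked terms.
2. Criteria: 9 matched to a term + 1 unmatched (superficial punctate keratitis) = 10 criteria.
3. Of the two terms without a criterion, secondary IOL intervention is picked up by a separate, unasterisked entry for unplanned secondary surgical intervention. Dim-light difficulty has no such cover. No criterion mentions dim light, night or mesopic function, and no redaction mark appears in the criteria list where one might be hidden.
4. Neighbouring optical symptoms in the same list (glare or halos, ghost images, reduced contrast sensitivity) are unasterisked and so reportable without a threshold. Dim-light difficulty is handled differently from its closest relatives, and no reason is given.
5. Sections 12.5.1 and 12.5.2 side by side: if the footnote governs, dim-light difficulty never has to be entered. If the all-AE rule governs, it always has to be, but then the footnote has no effect on any of the 11 terms. No sentence in the protocol settles which applies.
6. Appendix D records that the first amendment widened section 12.5.2 to all AEs. It lists no change to the asterisks or the footnote. That may be how the conflict arose, though the documents do not say so.

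**The case against.** The strongest reply is that the footnote is permissive and section 12.5.2 is mandatory. A careful site would record a subject's complaint about dim light, and nothing forbids it. This stands. A reader might infer that the term is bound to show zero events, but the documents support only an unresolved contradiction.

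A reader might also take dim-light difficulty to be the very risk the sponsor flagged for the Test lens. The visible text of section 12.4 names reduced quality of distance vision and low-light conditions, and the low-light symptom itself is redacted. The match is plausible but inferred.

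Nor do the documents show that low-light effects go unmeasured. The neighbouring optical symptoms stay reportable, and loss of BCVA has its own criterion. Appendix B refers to mesopic illumination in acuity testing, and the exploratory and several safety variables are redacted. The gap is in one AE term.

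Two other entries may look like further under-reporting. Secondary IOL intervention is not, because of the unasterisked entry noted above. The pain criterion, "Pain, per subjective patient reporting, graded on a VAS pain rating scale (from 0 to 10", gives no cut-off, and its natural reading leads to more reporting rather than less.

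Finally, the footnote applies equally to all three arms, so it does not by itself favour the Test lens.

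**Conclusion.** The point holds in this limited form. One asterisked AE term out of 11 has no reporting criterion and no cover elsewhere in the list, and the footnote that governs it conflicts with the rule that all AEs are entered in the CRF. The AE comparison between arms may therefore under-count that term or record it inconsistently.

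No numerical size can be given. The documents state no expected rate for the symptom, and section 13.2.1 plans descriptive tables without confidence bounds, so any count of lost events or upper limit on the rate would rest on an assumed figure. The primary endpoint, its hypotheses, the analysis sets and the sample size are untouched. This is a drafting inconsistency worth correcting because it is cheap and because unrecorded symptoms are hard to recover later. It does not threaten the trial's main conclusion.

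The conclusion assumes that the criteria list is complete as printed. Its particular relevance to the Test lens assumes that the redacted low-light symptom in section 12.4 is related to difficulty with tasks in dim light.

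**What to change.** Reconcile the anticipated-AE list, the footnote criteria and section 12.5.2:

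- Remove the asterisk from the dim-light term in section 12.5.1, so that it is reported under section 12.5.2 like the other optical symptoms.
- Add a sentence stating how the footnote relates to the all-AE rule, so that sites know which governs for the terms that keep an asterisk.

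Carry both into the CRF completion guidelines. The cost is protocol and guideline wording and a few more AE entries. The change should be in place before data collection.

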#### **12.5.4.2 Reporting Device Deficiencies**

A device deficiency is defined as an inadequacy of a medical device with respect to its identity, quality, durability, reliability, safety or performance. Device deficiencies include malfunctions, use errors, and inadequate labeling.

Principal Investigator must evaluate, record, and report any complaints/deficiencies or malfunctions experienced with an investigational medical device or Control or Comparator lens during this trial to the Sponsor and its representative promptly. The Sponsor shall review all device deficiencies, and, upon the Sponsor's request, Principal Investigator must supply any additional information related to the safety reporting of a particular event.

If the device deficiency is associated with or caused an SAE, then the SADE reporting procedure and timelines must be followed as per Section [12.5.4](#) in addition to device deficiency reporting procedures.

If no SADE was associated with or caused by the device deficiency but the deficiency might have led to a SADE if suitable action had not been taken or intervention had not been made or if the circumstance had been less fortunate, then deficiency needs to be reported within 24 hours of awareness and further reporting requirements to Regulatory Authority or to IRB/IEC need to be followed as applicable.

Any deficiency related to marketed products, including provided ancillary medical devices should be reported by the Principal Investigator to the sponsor or its representative as described above and to the Regulatory Authority, and to other parties in accordance with local requirements.

Details for submission of device deficiencies to sponsor or its representative are described in the Device Deficiency Reporting Form.

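### Section 12.5.1 gives conflicting instructions on reporting a re-operation after a lens-power calculation or use error, so such an event could be left out of the by-lens AE tables

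*Combined protocol and SAP*

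**What the plan says.** Section 12.5.1 of the combined protocol and SAP lists anticipated AEs and marks some with an asterisk. Of the marked events it says: "These events may be considered normal or expected events after cataract surgery and only need to be reported as AEs/SAEs if present as specified below". One of them is "Incorrect IOL power resulting in secondary surgical intervention", and the matching criterion is "Postoperative refractive error different from predicted, and not due to calculation or other use error, resulting in secondary surgical intervention". The entry for repositioning, exchanging or removing a lens is also asterisked, but no criterion in the list that follows is written for it.

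The same section defines an ADE and adds: "This definition also includes any event resulting from use error or from intentional misuse of the investigational medical device". It extends the definition to the Control and Comparator lenses. The anticipated list also has an entry without an asterisk: "Events resulting in unplanned secondary surgical intervention other than paracentesis to relieve pressure prior to 1 week postoperative or Nd:YAG capsulotomy".

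Section 12.5.2 requires all AEs, serious or not, to go in the CRF. Section 12.5.4.2 sets up a separate route for device deficiencies and states: "Device deficiencies include malfunctions, use errors, and inadequate labeling". Section 13.2.1 tabulates AEs by treatment group, severity and relationship to the lens, counting subjects. Section 13.7.1 analyses the Safety set by the lens received.

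**The concern.** Consider two subjects whose lens is exchanged because the refraction missed its target. In the first, nobody can explain the miss. In the second, the power was miscalculated or the wrong power was implanted. Under the asterisk rule and its criterion the first needs reporting and the second does not. Under the ADE definition and the general entry for unplanned secondary surgery, both belong in the AE data.

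What is at stake is the count of secondary interventions in the safety tables. Section 12.4 names secondary surgery as a risk and says that explantation of the Test lens may become necessary, so the safety analysis should capture this outcome fully. The exemption also turns on a judgement of cause made before the event is captured. Section 12.5.3 has the Principal Investigator evaluate AEs, and Section 9.1.1.1 leaves the Principal Investigator and the implanting Sub-Investigators unmasked. Section 11.1.1 requires standard-of-care measurements reused for screening, the lens power calculation among them, to be done by an investigator in the trial. In some cases, then, the person who classifies the error could be the person who made the calculation. The documents do not say that this holds generally.

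**Working it through.** The point rests on no alpha, power, sample size or margin in the plan, so there is no stated figure to reproduce. The check compares the texts and adds a small illustration.

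**1. Is a calculation error a use error in the plan's own terms?** Yes. The criterion in "Postoperative refractive error different from predicted, and not due to calculation or other use error, resulting in secondary surgical intervention" treats calculation as one kind of use error, so the use-error sentence in the ADE definition reaches it.

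**2. What does each provision say about a lens exchange after such an error?**

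| Provision | Result |
|---|---|
| 12.5.1, asterisk rule with the refractive-error criterion | Need not be reported |
| 12.5.1, asterisked entry for lens repositioning, exchange or removal | Unclear: the reader is sent to a criterion that is not there |
| 12.5.1, ADE definition | Included, for all three lenses |
| 12.5.1, entry without asterisk for unplanned secondary surgery | Included; its only exceptions are early paracentesis and Nd:YAG capsulotomy |
| 12.5.2, all AEs in the CRF | Included |
| 12.5.4.2, device deficiency | Captured, on a separate form |

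The same event is therefore exempt under one rule and reportable under three others.

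**3. Is the exclusion consistent with its neighbours?** No. The criteria for a damaged lens and for decentration or tilt also depend on a secondary intervention, and neither excludes by cause. A lens damaged through use error and exchanged meets its criterion. A lens of the wrong power through use error and exchanged does not.

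**4. Does the device-deficiency route repair the tables?** Not on the text available. Section 13.2.1 is built on AEs, and Section 13.2 describes no table of device deficiencies. Some safety variables in Section 12.3 are blacked out, so a separate count of secondary interventions cannot be ruled out. The conflict over AE reporting would remain even then.

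**5. How much would one missed subject change?** Section 9.1 plans about 30 Test, 30 Active Comparator and 20 Control subjects. Exact (Clopper-Pearson) 95% limits are used. With zero events in n subjects the upper limit is 1 − 0.025^(1/n).

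- n = 30: 1/30 = 3.3% (0.1% to 17.2%) becomes 0/30, with upper limit 1 − 0.025^(1/30) = 11.6%.
- n = 20: 1/20 = 5.0% (0.1% to 24.9%) becomes 0/20, with upper limit 1 − 0.025^(1/20) = 16.8%.

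**6. How likely is it that the case arises?** The documents give no rate. For an assumed per-subject rate p, the chance of at least one case among 80 subjects is 1 − (1 − p)^80. That is 33% at p = 0.5% and 91% at p = 3%. The answer is governed by the assumption, so no expected count is claimed.

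**The case against.** The strongest reply is that the plan read as a whole already captures these events. The entry without an asterisk covers a lens exchange for a wrong power, Section 12.5.2 asks for all AEs, and a device deficiency associated with an SAE goes to expedited reporting. This stands to the extent that a reader might infer that the plan simply drops such exchanges, and the documents do not support that. The reply does not remove the conflict. The asterisk rule is the more specific instruction, and an investigator can reasonably follow it over a general one.

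A reader might also infer that serious events go missing. That goes too far. Under Section 12.5.1 a surgical intervention makes an event serious only where there is serious deterioration in health and the surgery is done to avert a threat to life or vision or a permanent impairment. An exchange for a refractive miss may or may not qualify.

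A third tempting reading is bias between lenses, on the ground that a new optic with a draft IFU (Section 10.4) is more prone to power errors. The documents do not show this. They make no comparison of how well power calculation works for the three lenses, and Section 10.1 calls the Control lens the parent of the Test lens. If the Test lens missed its predicted refraction although the calculation was done correctly, the event would meet the criterion as written. If the instructions for use were at fault, the ADE definition would cover it. Mislabelling a true lens effect as a calculation error is possible, but that is conjecture.

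Finally, the safety analysis is descriptive, and neither the primary endpoint nor its power is touched. That is correct and limits the weight of the point.

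**Conclusion.** The point holds as a conflict in the reporting instructions. Section 12.5.1 exempts a secondary surgical intervention after a calculation or use error under one rule. It includes the same event under its ADE definition and its general entry for unplanned secondary surgery, and Section 12.5.2 includes it as well. A potentially serious event could therefore be left off the AE CRF and out of the by-lens AE tables. Omission is possible, not certain.

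The size is one subject at a time: 3.3 percentage points in a group of 30, or 5.0 in a group of 20. This assumes the planned group sizes and that the investigator applies the specific criterion. A difference between lenses is possible but not shown. The plan should be changed because the tables are small enough for one omission to turn an observed event into none, and because the change is cheap.

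**What to change.** - In the Section 12.5.1 criterion, delete the clause between the two commas, so that any refractive miss leading to secondary surgery is reported whatever its cause.
- In the same edit, reconcile the asterisked entry for lens repositioning, exchange or removal with the entry without an asterisk for unplanned secondary surgery. Every unplanned secondary surgical intervention, other than the two exceptions already listed, should be reported as an AE for all three lenses. Deleting the clause alone would leave this ambiguity in place.
- Record cause (calculation error, use error, unexplained) as an attribute of the AE.
- In Section 13.2.1, add a table of secondary interventions by lens, with and without use-error cases.
- Leave seriousness to the existing criteria in Section 12.5.1.

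The cost is a short edit to the plan, one field on the AE form and one table. The downside is small: a few user errors unrelated to the lens will appear in the AE tables, labelled by cause.
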